Appendix C (The IRB-approved Protocol)

Objective 1: Identify and characterize factors affecting children's exposures to chemical ingredients from consumer products found in their everyday environment in order to support the data and modeling needs of the exposure components of EPA's national research programs

The data analysis goal for objective 1 is to identify predictive factors associated with children's exposures to chemical and biological contaminants in their residential environments, with a focus on consumer product chemicals. Exposure factors of interest include housing characteristics, human activity, consumer product presence/use, and environmental contaminant concentrations and distributions. Exposure factor assessment will inform development and evaluation of exposure models for children. Identification of predictive factors that differ between green and traditional housing may also enhance CDC's ability to examine asthma outcomes in the Green Housing Study. Data analyses for this objective will be integrated with those for other objectives (particularly objectives 2, 4, 5, and 8).

Descriptive and summary univariate statistics will be compiled for measurement and survey data to identify variables with sufficient measurable results and variability to consider in factor analysis. Spearman/Pearson correlation analyses will be performed within and between all measurement data to elucidate relationships and associations. Geometric mean and geometric standard deviations will be calculated for target analytes by sibling/age groups. T-tests and/or F-tests of differences between measurement distributions across sibling/age group and other categorical product, housing, and activity factors will be calculated. In some cases, factor assessment by survey and activity data categories may require non-parametric tests. Where there are sufficient data, regression model analysis with target analyte measurements as outcome variables and product, activity, location, and housing variables as potential exposure factors will be constructed to examine relative contributions to variability in children's exposures. A specific goal of the analysis is to determine how, and to what extent, child activity factors might influence relationships between environmental contaminant levels and exposures as measured from hand wipe, sock, and biomarker concentrations.

Appendix C (The IRB-approved Protocol)

Objective 2: Evaluate the pilot study data metrics for incorporation in and enhancement of CDC's ability to understand the relationship between environmental exposures and asthma in green versus traditional low-income housing

There are two elements for addressing Objective 2. First, the quality and suitability of measurement and survey data collected using the pilot study protocol will be evaluated. Second, for metrics found to be of adequate quality and suitability, EPA proposes to work with CDC to explore how incorporation of the additional exposure data may enhance the understanding of relationships between environmental exposures and asthma in renovated and traditional housing in the Green Housing Study.

Environmental, personal, and biological measurement data quality will be assessed by examining several factors including completeness, precision, accuracy, and percent measurable. Quality assurance objective criteria have been set for several factors: completeness (90%), precision ($\pm 25\%$), and recovery (70 – 130%). Ideally, for a given analyte, the percentage of samples with analysis results greater than the limit of detection (or method limit of detection) will be $>50\%$ to facilitate estimation of relevant distributional parameters and to support data analyses including assessment of differences between groups, correlations, and linear regression modeling. Descriptive statistics for the measurement data will be used to document concentrations of target analytes found in the indoor environment. Comparisons to measurement data collected in other observational human exposure measurement studies will be completed.

Survey data include questionnaire responses, activity data, housing data, and product data. An important part of the pilot study is to assess the completeness and quality of survey data. To address the objectives in this research protocol, several approaches (e.g., barcode scanning, product photograph inventory, GPS, accelerometer) are being employed to collect personal, housing, and community exposure factor information for children. Results from traditional survey methods will be compared to collected data. For the questionnaire results, data quality analyses will be completed (as described in objective 8). There are several factors that will be examined to assess quality and suitability for use of the survey variables in exposure assessment. One goal is a $>90\%$ completeness rate for each survey variable. Comprehension and ability to provide requested information will be assessed through discussions with the field study team. Survey data will be examined to ensure that there exists a sufficiently diverse response range to be useful in distinguishing characteristics and activities where relevant in data analysis. The activity and location data collected using the questionnaire will be compared with the GPS and accelerometer data. Consumer product photographic inventory results will be compared to barcode scanning results for the products.

Following the initial step of assessing the measurement data quality and suitability for exposure assessment, EPA proposes to work collaboratively with CDC in exploring how the use of selected pilot study metrics may enhance the understanding of relationships between environmental exposures, activity, and asthma in the main Green Housing Study. The pilot study metrics, including the additional environmental measures and activity information, could be additional explanatory variables for asthma or could modify relationships for variables already collected in the main Green Housing Study. A goal of this evaluation is to identify which metrics may be candidates for incorporation into the full protocol at future Green Housing

Appendix C (The IRB-approved Protocol)

Study sites. Pilot study metrics can be assessed directly for relationships with asthma metrics at this study site. They can also be incorporated into multivariate regression models. A key limitation will be the relatively small sample size at the single study site. While this exploratory analysis may be suggestive of relationships, there may not be sufficient statistical power for desired levels of confidence. However, this exploratory analysis may inform decision-making regarding incorporation of pilot metrics into future sites of the main Green Housing Study.

Objective 3: Compare multimedia measurements and survey data between pre- and post-renovation time points in green and traditional low-income housing to assess exposure-related changes in the residence and participants due to renovation activities

Indoor air, house dust, soil, hand wipes, socks, duplicate diet, and the biomarkers will be analyzed for the priority chemical analytes identified in Table 6. House dust will also be analyzed for the priority biological analytes identified in Table 6. Descriptive and univariate statistics will be used to describe the results for individual chemical/biological target analytes, media types, time points, and renovated/non-renovated housing. Analyses will also be conducted to describe the summarized results for each time point. The statistical analyses conducted to address objective 8 (children's activity information) will also be used for this objective.

When data from post-renovation time points become available, statistical analyses (t-tests, correlations) of pre- and post-renovation time points will be conducted for targeted chemicals, media type, and time point. Similar tests will be performed to assess differences between renovated and non-renovated homes. Analyses (t-tests, correlations) comparing siblings living in the same home will also be conducted. The multimedia measurements, activity information, and other extant data will be employed to estimate children's aggregate and cumulative exposures to selected target chemicals.

Using the systems approach for the holistic child framework developed at the EPA, we anticipate exploring the inter-relationships between chemical and non-chemical stressors (e.g., activity patterns, housing factors) and asthma to the extent that sample sizes allow.

Objective 4: Evaluate exposure to chemicals in household cleaning and personal care products as a modifying factor in interpreting the effectiveness of green housing renovations on reducing the incidence of asthma-like symptoms

Using the consumer product inventory obtained through objective 7, specific chemical ingredients will be gleaned from a publicly available household product ingredients database and from measurements reported by Dodson et al. (2012). Human exposure models will combine the usage frequency questionnaire responses with the inventories to predict anticipated residential concentrations. A select set of indicator chemicals will be used to evaluate this extrapolation through statistical analysis of the relationship between consumer products found in the home and measured chemical concentrations (objective 5). Multiple regression models will then be used to examine the association between the primary risk factor (renovation status) and the outcome (symptom incidence). If inclusion of a possible modifying variable (predicted or measured

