Appendix C (The IRB-approved Protocol)

Primary objectives:

- 1) Identify and characterize factors affecting children's exposures to chemical ingredients from consumer products found in their everyday environment in order to support the data and modeling needs of the exposure components of EPA's national research programs;
- 2) Evaluate the pilot study data metrics for incorporation in and enhancement of CDC's ability to understand the relationship between environmental exposures and asthma in green versus traditional low-income housing;
- 3) Compare multimedia measurements and survey data between pre- and post-renovation time points in green and traditional low-income housing to assess exposure related changes in the residence and participants due to renovation activities.

Objective 1 will examine how influential personal, housing, and community factors are in determining children's exposures. Results will be used to directly compare siblings and determine how personal and housing factors vary. For siblings living in the same household, we hypothesize that shared exposures to housing and community factors both before and after building renovation will be similar. Thus, we hypothesize that personal exposure factors, including activities and behaviors, will most influence exposure to chemical and biological agents found in their indoor environment. Furthermore, the variability in personal exposure factors will be a function of age, lifestage, and health status (asthma versus no asthma). We can use this information to parameterize, refine, and evaluate exposure and dose models for consumer product active ingredients. Because of the lack of data on personal, housing, and community factors from the same cohort, it is necessary to collect these data to evaluate this objective.

Objective 2 will evaluate the pilot study methods and approaches for measuring exposures to consumer product chemicals and identifying exposure factors. It will also establish suitability for incorporation in future Green Housing Study sites and for future research directions. Our data collection effort is intended to complement the multimedia measurements and information being collected by CDC in the Green Housing Study. Methods found to be suitable in the pilot study will allow EPA and CDC to improve the evaluation of relationships between environmental exposures and asthma in the renovated and non-renovated homes.

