Appendix C (The IRB-approved Protocol)

Objective	Measurements Required	Proposed Analysis Approach

3) Compare multimedia measurements and survey data between pre- and post-renovation time points in green and traditional low-income housing to assess exposure-related changes in the residence and participants due to renovation activities
	
Chemical concentrations in available media (all chemicals, all media); mold information; activity information; all time points of data available for renovated and non-renovated homes; pre- and post-renovation information
	
Descriptive statistics; univariate statistics to compare chemical concentrations and mold at each time point and across renovated and non-renovated homes; correlations amongst chemicals and media; geometric mean and standard deviation for consumer product analytes in personal, residential, and biological samples by pre- and post-renovation time points; t-tests of differences between pre- and post-renovation time points; t-tests between siblings and pre- and post-renovation time points; non-parametric analysis of survey and activity response differences across time points and between renovated/non-renovated housing

4) Evaluate exposure to chemicals in household cleaning and personal care products as a modifying factor in interpreting the effectiveness of green housing renovations on reducing the incidence of asthma-like symptoms
	
Number of asthma-like symptoms reported by each participant; renovation status; total dust loading/air concentrations of measured cleaning product ingredients
	
Multiple regression models to examine the association between the primary risk factor (renovation status) and the outcome (symptom incidence) before and after including possible modifying factors (chemical concentrations). If inclusion of the additional variable causes the association between the primary risk factor and the outcome to change by 10% or more, then the additional variable is a potential effect modifier. Care will also be taken to assess any contributions to the outcomes of interest that are due to changes in medication and exposure-related behaviors rather than renovation.

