The ERMI values from the renovated homes will be compared to the traditional homes at each time point using regression analysis. Comparisons between the settled dust and EDC dust will be conducted both pre/post renovation and green versus traditional housing using Pearson correlations. For each child, respiratory data (FEV1%) will be evaluated in relationship to the ERMI value in the home using Pearson correlation analysis. Univariate and multivariate regression analyses will be used to explore different stressors as well as the interactions between different stressors.

Mold information will also be incorporated into statistical analyses to explore relationships between ERMI values in the homes at different times with asthma-like symptoms. The differences in concentrations in the dust samples of individual mold species at each time point will be evaluated using the Wilcoxon rank sum test. Corrections for multiple comparisons will be made using the Holms-Bonferroni test. This test will allow us to determine which mold species are significantly reduced by the renovations. Other analyses will compare the type of

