The design is stratified by city. As discussed below, one pair of housing developments will be chosen in each of 13 cities that meet the criteria delineated in section B1. We will frequency match green intervention and comparison homes by HUD-subsidized housing development, asthma status of children, age group of asthmatic children (7-12 years) and primary language spoken by mother/primary caregiver of the asthmatic child. We are not matching on ethnicity *per se*; however, much of the low-income housing in inner-city communities tend to be segregated to some extent, by race/ethnicity (Acevedo-Garcia and Lochner 2003). We will record race/ethnicity in our questionnaire and adjust accordingly in our analysis. As mentioned earlier, this selection will be limited by the availability of the ongoing HUD renovation efforts. There are no other problems requiring specialized sampling procedures. The data collection plan requires only one series of data collection within a one-year follow-up period.

Sample size overviews: Our calculations estimate that 416 subjects/study arm (i.e., green vs. comparison homes) must be recruited in order to achieve sufficient statistical power to statistically differentiate between the study arms (this paragraph outlines the calculations supporting this estimate, with details in subsequent paragraphs of this section; see also figure below). In order to have sufficient power to detect meaningful differences in both environmental

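### Objectives 3 and 9 attribute change to renovation but list only pre/post tests and separate between-arm tests; none compares change from baseline between the arms

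*Protocol*

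**What the plan says.** Objective 3 (Section 2.2 and Section 5.0) compares time points and housing types "to assess exposure-related changes in the residence and participants due to renovation activities". Two kinds of test are listed in Section 5.0:

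- Over time: "statistical analyses (t-tests, correlations) of pre- and post-renovation time points will be conducted for targeted chemicals, media type, and time point".
- Between housing types: "Similar tests will be performed to assess differences between renovated and non-renovated homes".

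Table 8 keeps the same split. It lists "t-tests of differences between pre- and post-renovation time points" and, separately, univariate comparisons at each time point across renovated and non-renovated homes.

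For Objective 9, Section 5.0 compares the mold index (ERMI) between renovated and traditional homes at each time point by regression, with no baseline term named. For species it says "The differences in concentrations in the dust samples of individual mold species at each time point will be evaluated using the Wilcoxon rank sum test", corrected by Holm-Bonferroni, and concludes "This test will allow us to determine which mold species are significantly reduced by the renovations".

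The design text promises something different. Section 2.1 says changes over follow-up will be compared and each home will be set against its own baseline. Appendix A, Part A (overview of the data collection system) describes a two-group pre-post comparison, within and between groups. Appendix A, Part B.1 says random assignment of the green intervention was not possible.

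**The concern.** The comparison homes are in the design to show what would have happened without renovation. That requires comparing the two arms on their change from baseline, and no test listed for Objective 3 or 9 does so.

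The listed tests have different weaknesses. A pre/post test within renovated homes cannot separate renovation from anything else that changed over the same months. A between-arm test at one visit cannot separate renovation from differences that existed beforehand, which matters when housing developments were selected rather than randomised.

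The mold sentence goes furthest because it states the conclusion. If the rank-sum test compares arms at one time point, it measures a difference in level, not a reduction. If it compares time points, it ignores the pairing within homes and has no control. On neither reading does it show that renovation reduced a species. At stake are the attribution in a primary objective and the list of species reported as reduced.

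**Working it through.** **1. The plan's own figure.** Section 2.3 gives a detectable limonene difference of 11.9 µg/m³ (SD 19.4, 35 per group, design effect D = 2.0, correlation ρ = 0.3, 80% power, alpha 0.05). The repeated-measures formula in Appendix A, Part B.1, solved for the difference, is

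d = √[ D × 2 × (z_α + z_power)² × {1 + (n − 1)ρ}/n × SD² / m ].

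With one-sided z_α = 1.645, z_power = 0.842, n = 3 and m = 35:

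d = √[ 2 × 2 × 2.487² × (1.6/3) × 19.4² / 35 ] = 11.9.

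The figure reproduces. One-sided alpha and n = 3 are inferred, since Section 2.3 states neither. It is a between-group difference averaged over three measures, not a difference in change, so the sample size example does not address the renovation contrast either.

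**2. Inputs for the error rates.** From the documents: 32 homes per arm (Section 2.1) and ρ = 0.3 (Section 2.3). Assumed: no renovation effect, normal data in SD units, two-sided 5% tests, no clustering, shifts of 0.3 to 0.5 SD. The documents give no shift sizes.

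**3. Pre/post paired t-test in the renovated arm, shared shift s.** SD of change = √{2(1 − 0.3)} = √1.4 = 1.18. Non-centrality = s / (1.18/√32), 31 df.

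- s = 0.3: non-centrality 1.43, significant in 28.5%.
- s = 0.5: non-centrality 2.39, significant in 63.9%.

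**4. Between-arm t-test at one follow-up, persisting arm difference δ.** Non-centrality = δ / √(2/32) = 4δ, 62 df.

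- δ = 0.3: non-centrality 1.2, significant in 21.9%.
- δ = 0.5: non-centrality 2.0, significant in 50.4%.

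**5. Between-arm test of change.** A shared s and a persisting δ both cancel. In 20,000 simulated data sets per scenario (s up to 0.75 SD, δ up to 0.5 SD) the rejection rate was 4.5% to 5.4%.

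**6. Precision.** Variance factor per home for one follow-up: single-visit level 1.0; unadjusted change 2(1 − 0.3) = 1.4; baseline-adjusted 1 − 0.3² = 0.91. For limonene with the plan's D = 2.0 and m = 35, two-sided, the detectable differences are 18.4, 21.7 and 17.5 µg/m³. Baseline adjustment thus avoids the loss. However, if δ persists unchanged, adjustment removes only ρδ and leaves (1 − 0.3)δ = 0.7δ, for example 0.35 of an initial 0.5 SD.

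**7. Number of tests.** Table 6 has 6 × 5 + 5 × 9 + 4 × 9 = 111 chemical analyte-medium pairs. Section 4.4 and Table 7 make duplicate diet (6 + 5 + 4 = 15), blood (5 + 4 = 9), toenail (5) and feces (5) baseline-only. That leaves 111 − 34 = 77 pairs, 77 × 3 = 231 tests over three follow-ups, and 231 × 0.05 ≈ 12 expected false positives before any bias.

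**The case against.** The strongest reply is that the right contrast is already in the protocol. Section 2.1 compares each home with its own baseline, Appendix A describes a two-group pre-post comparison, and Section 5.0 announces longitudinal analyses. The words on similar tests between housing types could even be read as tests of the pre/post differences, and the ERMI regression might include baseline. This is a pilot of fixed size, and model detail commonly belongs in a statistical analysis plan. That shows the intent, and the fix can rest on it. But Table 8 and Section 5.0 name the tests and do not carry the intent through, and the mold sentence states an inference its test cannot support. Pilot status does not excuse that.

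Other parts of the reply limit the point:

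- **Season at every visit.** A reader might infer that all pre/post tests are seasonally biased. Renovation takes a few days, so baseline part 2 falls within weeks of baseline, and 12 months returns to about the same season. The exposed visit is mainly 6 months. Comparison homes are measured within one week of their matched home at baseline and baseline part 2, so season should not bias between-arm tests there.
- **Pre-existing differences.** Arms are frequency matched, and Section 2.1 draws both from the same development or neighborhood. The statement "one pair of housing developments will be chosen in each of 13 cities" belongs to the 13-city parent plan. Matching reduces imbalance but does not remove it.
- **Siblings and visits as independent samples.** The text does not say this. It does not state whether the t-tests are paired, and sibling comparisons are described within the same home.
- **Multiplicity.** Multiplying all 111 pairs by three follow-ups gives 333 tests and about 17 false positives, but 34 pairs have no follow-up sample.
- **A guaranteed 5%.** Section 2.3 assumes a design effect of 2.0. If that applied to change scores and were ignored, the critical value would shrink to 1.96/√2 = 1.39 and about 17% of tests would reject.

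**Conclusion.** The point holds as an error in the stated analysis for Objectives 3 and 9: attribution to renovation rests on tests that do not isolate it, in non-randomised homes, and Section 5.0 does not match Section 2.1. The sizes are about 28% to 64% for the pre/post test and 22% to 50% for the single-visit between-arm test, against about 5% for the change contrast. They depend on the assumed 0.3 to 0.5 SD shifts, correlation 0.3, 32 homes per arm and no clustering, and they illustrate rather than predict. Each test carries its own bias, so the two ranges should not be added. The change contrast removes shared trend and fixed differences; it does not remove trends that differ between arms. Multiplicity is secondary, at about 12 expected false positives in 231 tests.

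**What to change.** - For Objectives 3 and 9, define the renovation effect as the between-arm difference in change from baseline, on log concentration for the analytes. Estimate it with a baseline-adjusted or arm-by-visit mixed model. Include a random effect for home (child within home for personal and biological samples) and an allowance for building or development clustering consistent with the design effect in Section 2.3.
- Report the unadjusted change contrast alongside any baseline-adjusted estimate, because adjustment only partly removes imbalance between non-randomised arms.
- For molds, apply the rank-sum test to each home's change from baseline, renovated against comparison, keeping Holm across species. Rewrite the sentence on species reduced by renovation to match.
- Label single-arm and single-time-point tests descriptive, and reconcile Table 8 and Section 5.0 with Section 2.1.

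The cost is analysis wording only: the four visits and concurrent comparison homes are already planned. An unadjusted change score is less precise (1.4 against 1.0 per home). An arm-by-visit random-intercept model does not by itself recover this when data are complete; baseline adjustment does (0.91).

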Appendix C (The IRB-approved Protocol)

2.3 Sample Size Considerations

The sample size for the EPA pilot study add-on is fixed and dependent on CDC's grantee's ability to recruit and retain participants. Using available chemical concentration data for limonene (Sarigiannis et al., 2011), we can estimate the effect sizes we can see given various sample sizes (assumptions: design effect = 2.0, statistical power = 0.8, alpha level = 0.05, correlation = 0.3).

Example: Limonene in air ($\mu\text{g}/\text{m}^3$)

If non-renovated homes have a mean concentration and standard deviation = $15.0 \pm 19.4 \mu\text{g}/\text{m}^3$, with a fixed sample size of $n=35$ participants in each group (renovated and non-renovated homes), we could see a minimum size difference of $11.9 \mu\text{g}/\text{m}^3$.

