Appendix C (The IRB-approved Protocol)

For the comparison homes, the correlations between baseline and 3-month follow-up cockroach allergen measurements and 3-month and 6 months follow-up measurements were approximately equal to 0.5.

Design effect due to clustering = 3.62

Equation 1. Sample size for repeated measures – cockroach allergen.

$$m = D * [2(z_{\alpha} + z_{Q})^2 \{1 + (n - 1)\rho\}] / (n\Delta^2)$$

m = number in each group (e.g., intervention and non-intervention)

n = number of repeated measurements (equals 3 in this scenario)

z_{α} = Z score for alpha = 0.05

z_{Q} = Power, set at 0.80

ρ = correlation among repeated observations

$\Delta = d / \sigma$ where d is the smallest meaningful difference and σ is the standard deviation

D = Design effect due to clustering of apartments within buildings (This was not in the formula used by Diggle et al. (1994), but was added to adjust for clustering expected in our study.)

Note: we also assumed a design effect (e.g., increase (multiplicative) sample needed because of the effects of clustering) equal to 3.62. This is the ratio in clustering sampling variance divided by the simple random variance (of the same size) (i.e., the denominator without clustering taken into account).

When calculating the sample sizes, we used two standardized effect sizes based on the IPM study: 0.37 and 0.30. The effect size of 0.37 is based on the ability to detect a difference of 0.8148 ln units of the *Blattella germanica* cockroach allergen (i.e., Bla g 2) and a standard deviation of ~ 2.2. The effect size of 0.30 is based on the ability to detect a difference of 0.649 ln units of Bla g 2 and a standard deviation of 2.2. We also assumed an alpha of 0.05 and a power of 80%). The sample size based on changing the expected correlation between repeated measures would result is presented in Table 21.

Assuming a correlation of 0.5 we get the following:

With assumption 1, we would need 16 buildings (8 green and 8 comparison) with at least 25 apartments per building

With assumption 2, we would need 26 buildings (13 green and 13 comparison) with at least 25 apartments per building.

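### The sizing assumes a design effect of 2.0, but the renovated-versus-non-renovated tests named for Objectives 3 and 9 carry no clustering term; if 2.0 holds, a nominal 5% test has about a 12% to 17% false-positive rate

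*Protocol*

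**What the plan says.** **Sizing.** Section 2.3 lists "design effect = 2.0, statistical power = 0.8, alpha level = 0.05, correlation = 0.3" and states that 35 participants per group allow a difference of 11.9 µg/m³ in airborne limonene to be seen (SD 19.4). It does not define the design effect or the correlation, and it gives neither the number of visits nor the sidedness of alpha. The formula it appears to follow is Equation 1 in Appendix A, B.1, where D is clustering of apartments within buildings, ρ is correlation among repeated observations and three measurements are assumed. There the cockroach-allergen figure is "Design effect due to clustering = 3.62".

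**Analysis.** Section 5.0, Objective 3, names t-tests and correlations by chemical, medium and time point for the pre/post comparison, then says: "Similar tests will be performed to assess differences between renovated and non-renovated homes". Table 8 lists for the same objective "univariate statistics to compare chemical concentrations and mold at each time point and across renovated and non-renovated homes". For Objective 9, "The ERMI values from the renovated homes will be compared to the traditional homes at each time point using regression analysis", and individual mold species are compared at each time point by Wilcoxon rank sum test with a Holm-type correction. No building term, design effect or cluster-adjusted standard error is attached to any of these. Mixed models are named in Section 5.0 only under Objective 6, for a participant's biomarkers before and after renovation. Hierarchical models appear in the parent study's plan (Appendix A, B.2) and, in the pilot, only as draft approaches to community-level data under Objective 11.

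**Layout of the homes.** Section 2.1 plans 32 renovated and 32 comparison homes from the same development or neighborhood. Appendix A, B.1, says for the parent study that "one pair of housing developments will be chosen in each of 13 cities" and describes 32 subjects in each of 13 buildings per arm. It also allows a city with several smaller developments.

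**The concern.** A design effect in the sizing is a statement that homes in the same building are not independent and that the variance of the renovation contrast is twice what independent homes would give. A t-test or ordinary regression on the same homes computes its standard error as if they were independent. The planning and the named tests therefore rest on different variances. Under the planning assumption, the reported intervals and p-values for the renovation contrast would be too favorable.

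Objective 3 is a primary objective, and Section 2.2 hypothesizes significant differences under it. The test is repeated over many analytes, media and visits. Objective 9 intends to say which mold species renovation reduces; its multiplicity correction works on p-values that are already too small and does not repair them.

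The visit correlation raises a second, separate matter. It is what makes several visits per home more precise than one. Tests run one visit at a time do not use it, so the stated detectable difference does not describe them.

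**Working it through.** **Inputs.** From Section 2.3: SD 19.4 µg/m³, 35 per group, D = 2.0, ρ = 0.3, power 0.80, alpha 0.05. From Appendix A, B.1, Equation 1: n = 3 measurements. Normal quantiles: 1.645 (one-sided 5%), 1.960 (two-sided 5%), 0.842 (80% power).

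**1. Reproduce the plan's figure.** Solve Equation 1 for the difference:

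d = SD × √( D × 2 × (z_α + z_power)² × {1 + (n−1)ρ}/n ÷ m )

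With three visits the visit factor is (1 + 2 × 0.3)/3 = 0.533.

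- One-sided: 19.4 × √(2 × 2 × 2.487² × 0.533 / 35) = 11.91. This matches 11.9.
- Two-sided: 13.42.
- One-sided with 1, 2 or 4 visits: 16.31, 13.15 or 11.24.
- One-sided, three visits, no design effect: 8.42.

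Of the variants tried, only D = 2.0, ρ = 0.3, three visits and one-sided alpha give 11.9. Both terms are in the published figure.

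**2. Size of a test that ignores D.** If the true variance of the difference is D times the one used, the standard error should be √D times larger; √2 = 1.41. The actual size is

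two-sided: 2 × {1 − Φ(1.960/√D)}; one-sided: 1 − Φ(1.645/√D)

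| D | Source of value | Two-sided | One-sided |
|---|---|---|---|
| 1.2 | parent study, asthma outcomes | 7.4% | 6.7% |
| 2.0 | Section 2.3 | 16.6% | 12.2% |
| 3.62 | parent study, cockroach allergen | 30.3% | 19.4% |

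At D = 2.0, t quantiles with 62 to 68 degrees of freedom give 16.3% two-sided. Simulated two-sided t-tests on 32 versus 32 clustered homes, with 1 to 16 clusters per arm and D = 2.0, give 16.5% to 17.2%.

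**3. Cost of testing one visit at a time.** Carry D = 2.0 but use a single visit:

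SE = 19.4 × √(2 × 2/35) = 6.56, and 11.9/6.56 = 1.81

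- Power one-sided: Φ(1.81 − 1.645) = 57%
- Power two-sided: Φ(1.81 − 1.960) = 44%
- Detectable difference: 16.3 one-sided, 18.4 two-sided

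The three-visit mean gives 80% one-sided and 70% two-sided. A per-visit test that leaves out the visit correlation loses precision but keeps its size.

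**4. What inflating the standard error by √2 can and cannot do.** If D is really 2.0, it restores 5%. If an arm is one building of 32 homes with an intraclass correlation of 0.05 (an illustrative value), D = 1 + 31 × 0.05 = 2.55, and the two-sided size after inflation is 2 × {1 − Φ(1.960 × √(2/2.55))} = 8%. At D = 3.62 it is about 15%.

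**The case against.** **The plan is open-ended, and standard-error methods often sit in a SAP.** Section 5.0 promises longitudinal analyses and leaves more complex ones to data quality, and the covariates of the Objective 9 regression are unspecified. That is fair as far as it goes. But the protocol does not leave the renovation contrast blank. It names tests, and followed as written they contradict the variance it planned with.

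**A flat 17% might be inferred.** The documents do not support that. It needs a two-sided test and a true design effect of 2.0. Objective 3's hypothesis is non-directional, which favors two-sided, yet the 11.9 µg/m³ reproduces only one-sided, where the rate is 12%. The design effect is a planning value. The parent study uses 1.2 for asthma outcomes and about 3.6 for environmental analytes, including piperonyl butoxide, which is also a pilot target.

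**It might also be inferred that ignoring the visit correlation adds to the false positives.** It does not in a single-visit test; step 3 shows a loss of power only.

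**Nor is one building per arm established for this site.** That reading comes from the 13-city appendix. Section 2.1 requires only the same development or neighborhood, Appendix A matches comparison homes to intervention homes, and no building count is given. If renovated and comparison homes share buildings, the building effect largely cancels and a plain t-test may be close to nominal or conservative. This part of the objection stands, and it makes the size conditional.

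**This is a fixed-sample pilot that admits its limits.** True, but the caution about suggestive, exploratory findings in Section 5.0 concerns Objective 2. A small sample is also no reason to report intervals narrower than the plan itself believes.

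**Conclusion.** The mismatch is real: the sizing carries a clustering term, and the renovated-versus-non-renovated tests named for Objectives 3 and 9 carry none. If the protocol's design effect of 2.0 holds, intervals are too narrow by a factor of 1.41, and a nominal 5% test has a false-positive rate of about 12% (one-sided) to 17% (two-sided). Two-sided, the rate would be about 7% at D = 1.2 and 30% at D = 3.62. Separately, single-visit tests do not have the 80% power stated for 11.9 µg/m³; with clustering carried they have 57% one-sided or 44% two-sided.

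This rests on reading Section 2.3's terms as Equation 1 defines them, which the exact reproduction of 11.9 supports, and on renovation following buildings at this site, which the protocol does not settle.

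**What to change.** 1. Name the cluster unit, and record the building of every home.
2. For the main renovation contrast in Objectives 3 and 9, fit a baseline-adjusted repeated-measures model on the log scale over the post-renovation visits. Keep the time-point contrasts inside the model, since Objective 3 asks about change over time. Include a home effect, and child within home for personal samples and biomarkers. Treat building as a random effect, or use small-sample cluster-robust standard errors, where there are enough buildings.
3. Where an arm has only one or two buildings, multiply the standard error by the square root of the assumed design effect and show the result at other values, for example 1.2 to 3.6. State that building and renovation cannot be separated; the inflation allows for assumed extra variance but does not remove that confounding.
4. Label unadjusted single-visit tests as descriptive.

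The cost is analysis wording, some programming and a building identifier; no new samples are needed. The downside is intervals wider than those of the plain t-test and, with few buildings, possibly wider than Section 2.3 implies, because small-sample cluster methods use larger critical values.
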